4.2.5 PK data

The PK analysis of the serum concentration data for benralizumab will be performed by a third-party vendor, PPD.

The PK summaries, figures, and data listings will be produced by IQVIA. Additional population PK analysis will be performed by AZ.

Patients who have missing PK samples will be evaluated on a case-by-case basis. Any PK data available from patients excluded from the NCA population will be listed for each time point but not summarised. Any data to be excluded from the summary tables and figures for the PK analysis set will be clearly indicated. A deviation (gap between nominal and actual time points) column will be added into the listing of concentration data. The exclusion of any patients from the PK analysis set or from the analysis will be agreed by the study physician, statistician and PK Scientist during the data review meeting.

Serum concentrations and PK parameters will be summarized by treatment/weight group using appropriate descriptive statistics. Figures showing individual and mean of PK concentration-time profiles will be produced on both semi-log and linear scales. Serum concentration data associated with positive ADA status will be flagged in the PK concentration listings by safety analysis set and will be excluded from the summary statistics and mean profiles. If an entire concentration-time profile is below the lower limit of quantification (< LLOQ) the subject will be excluded from both NCA and PK analysis sets.

4.2.5.1 Non-compartmental /PopPK parameter analysis

Blood samples for determination of benralizumab PK parameters in serum will be taken at timepoints specified in Table 1 of the CSP. Benralizumab concentrations in serum will be analysed by a central laboratory on behalf of AstraZeneca, using a validated bioanalytical method. Full details of the analytical method used will be described in the bioanalytical report.

For all serum PK concentrations, values <LLOQ are replaced by a value of zero.

The PK parameters listed in section 3.2.1 will be derived using NCA set or PK analysis set. PK analysis, where possible, will be carried out using actual time recorded in the raw data. If actual times are missing, nominal times will be used.

The PK parameters will be derived using noncompartmental methods with Phoenix WinNonlin® (Certara USA, Inc.) Version 6.3 or higher and/or SAS® Version 9.2, or higher (SAS Institute, Inc., Cary, North Carolina), or via population PK (PopPK) method using NONMEM (version 7.3 or higher)

The following PK parameters will be derived:

- C_{max} Maximum benralizumab concentration obtained directly from the observed concentration versus time over 0-28days.
- t_{max} Time to maximum concentration obtained directly from the observed concentration versus time data.

- $AUC_{(0-28)}$ Area under the concentration-time curve from time zero to the time of the last quantifiable concentration at time “Day 28”, calculated by linear up/log down trapezoidal summation.
- $t_{1/2}$ Terminal half-life, calculated as $\ln(2)/$ terminal rate constant (λ_z).
- CL/F Apparent clearance (L/h), estimated as dose divided by AUC.
- $C_{\text{trough(W16)}}$ Trough concentration week 16, the lowest concentration reached by Benralizumab before the next dose is administered

Additional PK parameters applicable to the actual PK sampling time may be determined if deemed appropriate.

All data received will be presented in data listings. Descriptive statistics for the PK parameters C_{max} , t_{max} , $AUC_{(0-28)}$, $t_{1/2}$, and CL/F as well as C_{trough} week 16 for benralizumab will be presented using NCA or PK analysis set

Summary of PK parameters

Data from patients eligible for inclusion in the NCA and any samples taken outside of CSP scheduled time windows (as per CSP Table 1) will be included to determine the PK parameters. In the event where PK parameters cannot be estimated accurately using NCA, the PK parameters may be estimated via population PK approach using data from PK analysis set

All reportable PK parameter data for the patients in the NCA set or PK analysis set will be summarised and listed.

All PK parameters, excluding t_{max} , will be summarised by treatment/weight group using the following descriptive statistics:

- Number of observations (n)
- Gmean, calculated as $\exp[\mu]$, where μ is the mean of the data on a logarithmic scale
- gCV%, calculated as $100 \sqrt{[\exp(s^2)-1]}$, where s is the SD of the data on a log scale
- Amean
- SD
- Median (min, max)

For PK parameter t_{max} , only n, median, min and max will be produced.

Precision and rounding rules for PK parameters

PK parameter listings will be presented according to the following rules:

- C_{max} to be presented to the same number of significant figures as received from the bioanalytical laboratory
- t_{max} , t_{last} (time to last quantifiable concentration)
- $AUC_{(0-28)}$, $t_{1/2}$, , CL/F , all ratios of PK parameters and coefficient of determination adjusted (Rsq) which is the goodness of fit statistic for calculation of λ_z
- N to be presented as an integer (no decimals)

The descriptive statistics for PK parameter data will all be presented to at least 2 decimal places apart from the following:

- t_{max} : present as received in the data, usually to 2 decimal places
- n: present as integer

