3 OBJECTIVES AND ENDPOINTS

Study objectives and endpoints are shown in [Table 2](#).

Table 2 **Study objectives and endpoints**

| Primary objectives: | Endpoints/variables: |
|--|--|
| To evaluate the pharmacokinetics (PK) of benralizumab administered subcutaneously (SC) in children from 6 to 11 years of age with severe eosinophilic asthma | 
 ● Clearance ● Area under concentration time curve to Day 28 (AUC₀₋₂₈) ● Maximum serum concentration (C_{max}) ● Terminal phase elimination half-life (t_{1/2}) ● Time to reach C_{max} (T_{max}) |
| To evaluate the pharmacodynamics (PD) of benralizumab administered SC in children from 6 to 11 years of age with severe eosinophilic asthma | Change from baseline in peripheral blood eosinophil count at Weeks 4, 8, 12 and 16 (Part A), and Weeks 24 and 48 (Part B) |
| Secondary objectives: | Endpoints/variables: |
| To characterize the PK of benralizumab | Body weight-adjusted clearance |
| To evaluate the immunogenicity of benralizumab | Presence of anti-benralizumab antibodies |
| To evaluate the effect of benralizumab on pulmonary function | Change from baseline in pre-dose (when applicable), pre-bronchodilator, FEV ₁ measured at Weeks 4, 8, 12, and 16 (Part A), and Weeks 24 and 48 (Part B) |
| To assess the effect of benralizumab on asthma symptoms and other asthma control metrics | Change from baseline in ACQ-IA score, measured at screening and Weeks 1, 2, 4, 8, 12, and 16 (Part A), and Weeks 24, 32, 40 and 48, and at follow-up (Part B) PGIC-IA, measured at Week 16 (Part A), Weeks 24, 32 and 48 (Part B), and at the DXD/WD visit CGIC, measured at Week 16 (Part A), Weeks 24, 32 and 48 (Part B), and at the DXD/WD visit |
| Safety objective: | Endpoints/variables: |
| To assess the safety and tolerability of benralizumab | AEs Vital signs Collection of clinical chemistry/haematology parameters and urinalysis |
| Exploratory objective: | Endpoints/variables: |
| To evaluate exacerbations experienced | Annualized asthma exacerbation rate (AAER) |

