8.5 Pharmacokinetics

8.5.1 Collection of samples

Blood samples for determination of PK parameters in serum will be taken at timelines as specified in [Table 1](#). Blood samples taken at visits when a dose of benralizumab is administered must be taken pre-dose. Blood samples taken at visits when no benralizumab dose is administered may be taken at any time during the day of the visit. The time and date of blood samples taken for PK analysis must be recorded in the eCRF.

Samples will be collected, labelled, stored, and shipped as detailed in the Laboratory Manual.

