4.2.10	Asthma control questionnaire (ACQ-IA).....	35
4.2.11	Global impression of change.....	35
4.2.12	Safety Analysis.....	36
4.2.12.1	Adverse Events.....	36
4.2.13	Laboratory variables	37
4.2.14	Vital signs.....	38
4.2.15	ECG variable	38
4.2.16	Physical examinations.....	38
4.2.17	Exploratory analyses.....	39
4.2.17.1	Annualised asthma exacerbation rate	39
4.2.18	Subgroup Analysis.....	39
5	INTERIM ANALYSES	39
6	CHANGES OF ANALYSIS FROM PROTOCOL	40
7	REFERENCES	41
8	APPENDIX	42

LIST OF TABLES

Table 1: Visit windows for assessment.....	17
Table 2: Vital signs reference ranges for age 6 -11 years	23
Table 3: Vital signs reference ranges for age 12 -14 years	24

LIST OF FIGURES

Figure 1	Study Design	12
----------	--------------------	----

LIST OF ABBREVIATIONS

Abbreviation or special term	Explanation
ACQ-IA	Interviewer-administered asthma control questionnaire
ADA	Anti-drug antibodies
AE	Adverse event
ALT	Alanine aminotransferase
Amean	Arithmetic mean
AAER	Annualized asthma exacerbation rate
AST	Aspartate aminotransferase
ATC	Anatomical therapeutic chemical
ATS	American thoracic society
AUC	Area under concentration time curve from time zero extrapolated to infinity
AUC ₍₀₋₂₈₎	Area under the concentration time curve from time zero to 28 days after dosing
BMI	Body mass index
ClIs	Confidence intervals
CL/F	Apparent clearance for parent drug estimated as dose divided by AUC
C _{max}	Observed maximum benralizumab concentration
CGIC	Clinician global impression of change
CRF	Case report form (electronic)
CSP	Clinical study protocol
CSR	Clinical study report
CSRHLD	Corporate clinical study report or higher level document
CTMS	Clinical trial management system
CV	Coefficient of variation
CV%	Coefficient of variation
DAE	Adverse event leading to discontinuation of investigational product
DBL	Database lock
DBP	Diastolic blood pressure
DSMB	Drug safety monitoring board
DXD	Early discontinuation visit
ECG	Electrocardiogram
eCRF	Electronic case report form
ED	Emergency department
EOT	End of treatment
ERS	European respiratory society
FEV1	Forced expiratory volume in 1 second

Abbreviation or special term	Explanation
gCV%	Geometric coefficient of variation
GMean	Geometric mean
gSD	Geometric standard deviation
ICS	Inhaled corticosteroids
IP	Investigational product
Kg	Kilograms
LLOQ	Lower limit of quantification
M	Metres
Max	Maximum
MedDRA	Medical dictionary for regulatory activities
Min	Minimum
N	Number of patients
nAb	Neutralizing antibodies
NC	Not calculated

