4.2.5.2 Summary Statistics of PK serum concentrations

Serum concentrations will be presented by assessment day in tables and listings. The serum concentrations summaries will include:

- n
- $n < LLOQ$ ((n < LLOQ)/n at time point) *100%
- Gmean (gCV%)
- gSD Amean
- arithmetic standard deviation (SD), median (min, max)

For DXD, only the PK samples collected within one dosing cycle after last dose will be included in the summary statistics of schedule visits during treatment period.

The exclusion of concentration data from the PK analysis for an individual time point will be documented by the PK Scientist including the reason(s) for exclusion. These individual concentration data will also be excluded from the summary tables and corresponding figures.

For those patients eligible for inclusion in the PK Analysis set, the concentration-time data will be summarised by the scheduled time point. Any post-dose samples taken outside the window of the scheduled time will be flagged by the PK Scientist and excluded from the summary tables and figures but will be included in the PK analysis to determine the PK parameters.

Serum concentrations that are <LLOQ will be reported as follows:

Individual concentrations below the LLOQ of the bioanalytical assay are non-quantifiable and will be reported as <LLOQ in the listings with the LLOQ defined in the footnotes of the relevant tables, figures and listings. Non-reportable individual concentrations that is a PK parameter (e.g. C_{max}) will be listed as not reportable (NR) and concentrations that are missing

will be listed as no sample (NS) in the listings. Serum concentrations that are <LLOQ, NR or NS will be handled as follows for the provision of descriptive statistics:

- Any values reported as NR or NS will be excluded from summary tables and figures.
- All <LLOQ values will be substituted with a value of zero, and will be excluded from summary descriptive statistics.
- If all concentrations are <LLOQ at a time point, no descriptive statistics will be calculated for that time point. The Gmean, Amean, SD, min, median and max will be reported as <LLOQ and the gCV%, gSD, and SD as not calculated (NC).
- The number of <LLOQ values, n will be reported for each time point along with the total number of collected values (n).

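### SAP 4.2.5.1 lets AUC(0-28), a primary PK endpoint, end at each patient's actual Week 4 sampling time and gives no rule for bringing the area to 28.0 days

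*SAP*

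**What the plan says.** The documents describe the end of this interval in three places.

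- Protocol section 3, Table 2 lists the primary endpoint as "Area under concentration time curve to Day 28".
- The SAP list of abbreviations defines it as "Area under the concentration time curve from time zero to 28 days after dosing".
- SAP 4.2.5.1, the derivation rule, runs the area "to the time of the last quantifiable concentration at time “Day 28”, calculated by linear up/log down trapezoidal summation". In the same list, Cmax is "obtained directly from the observed concentration versus time over 0-28days", which is a fixed interval.

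The time basis is also in SAP 4.2.5.1: "PK analysis, where possible, will be carried out using actual time recorded in the raw data". Nominal times are used only where actual times are missing.

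Protocol Table 1 sets Visit 6 at Day 28 ±7 days. It is a dosing visit, and Protocol 8.5.1 states: "Blood samples taken at visits when a dose of benralizumab is administered must be taken pre-dose". The Visit 6 sample therefore closes the first-dose profile.

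For parameter derivation, SAP 4.2.5.1 also includes "any samples taken outside of CSP scheduled time windows". SAP 4.2.5.2 says that such samples are "excluded from the summary tables and figures but will be included in the PK analysis to determine the PK parameters".

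SAP 2.1.2 admits a patient to the non-compartmental (NCA) set with any three quantifiable samples out of Days 1, 7, 14 and 28.

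**The concern.** Taken together, these rules make the upper integration limit the patient's own last sampling time. That time can be anywhere from Day 21 to Day 35, or later if the sample still precedes the second dose. A quantity labelled as a 28-day area would then cover 21 days in one child and 35 in another. Neither document gives an interpolation or extrapolation rule to 28.0 days.

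AUC(0-28) is a primary endpoint, summarised by weight group with as few as 8 patients in a stratum. Differences in visit timing would enter individual values, the minimum and maximum, and the CV as if they were differences in exposure. The NCA is run by an external vendor (SAP 4.2.5), which needs one unambiguous rule. The planned listing of time deviations shows who is affected but does not correct the area.

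A related gap concerns patients who enter the NCA set on Days 1, 7 and 14 only. The plan does not say what their AUC(0-28) is, and an area to the last quantifiable sample would stop at Day 14.

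**Working it through.** The documents give no AUC figure to reproduce, so this checks how large the effect would be.

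**Inputs from the documents**
- Sampling on Days 0, 1, 7, 14 and T, where T is the Visit 6 day, 21 to 35 (Protocol Table 1).
- Linear-up/log-down trapezoids (SAP 4.2.5.1).
- Half-life: Protocol Table 5 equates 12 weeks with 5 half-lives, so 84/5 = 16.8 days.
- CV of 30% (Protocol 9.2) and a minimum stratum of 8.

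**Assumptions not in the documents**
- One compartment with first-order absorption.
- Absorption half-life of 1 to 5 days.
- Half-life of 12 to 20 days as a sensitivity range.
- The distribution of visit days.

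**Formulas** (concentration in units of dose over volume)
- C(t) = ka/(ka − ke) × [exp(−ke·t) − exp(−ka·t)], with ke = ln2/16.8 and ka = ln2/(absorption half-life).
- Rising interval: Δt(C0 + C1)/2. Falling interval: Δt(C0 − C1)/ln(C0/C1).

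**Area by closing day**

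| | Absorption half-life 1 d | Absorption half-life 5 d |
|---|---|---|
| Area to Day 14 | 0.244 + 3.831 + 4.816 = 8.891 | 0.063 + 1.962 + 3.926 = 5.951 |
| Add to Day 21 | 3.628, total 12.519 | 3.899, total 9.850 |
| Add to Day 28 | 6.346, total 15.237 | 7.024, total 12.975 |
| Add to Day 35 | 8.382, total 17.273 | 9.370, total 15.321 |
| Day 21 / Day 28 | 0.822 (−18%) | 0.759 (−24%) |
| Day 35 / Day 28 | 1.134 (+13%) | 1.181 (+18%) |
| Day 35 / Day 21 | 1.38 | 1.56 |

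Over half-lives of 12 to 20 days, the Day 21 ratio is 0.747-0.853 and the Day 35 ratio 1.098-1.199. An area stopped at Day 14 would be 8.891/15.237 = 0.58 or 5.951/12.975 = 0.46 of the 28-day area.

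**Group level, visits uniform over Day 21-35**
- The arithmetic mean shifts by −0.7% to −1.0%.
- Between 34% and 52% of patients are more than 10% off.
- The geometric CV from timing alone is 9.2-12.6%. Combined with 30% on the log scale, √[(1 + 0.092²)(1.09) − 1] = 31.5% and √[(1 + 0.126²)(1.09) − 1] = 32.8%.
- The standard error of the log mean with n = 8 and a 30% CV is √(ln 1.09)/√8 = 0.104. With timing added it becomes 0.109 to 0.113.

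If visit days instead have an SD of 2.5 days around Day 28, the total CV is about 31%, and 7-18% of patients are more than 10% off.

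**Ending the area at 28.0 days** (log-linear, using the slope of the last two samples)
- Absorption 5 d, sample on Day 21: slope ln(0.5946/0.5211)/7 = 0.0188 per day, C(28) = 0.457, area 13.268, ratio 13.268/12.975 = 1.023.
- Absorption 5 d, sample on Day 35: slope ln(0.5946/0.3248)/21 = 0.0288 per day, C(28) = 0.397, area 12.802, ratio 0.987.
- Absorption 1 d: both ratios are 1.000.

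The noise-free error is therefore −1.3% to +2.3%. A simulation of 200,000 profiles with uniform visits and 10-15% residual error also covers assay noise. The share of patients more than 10% off falls from 39-55% to 7-26%. The last two samples do not decline in 0.2-7% of patients overall and in 2-27% of those sampled on Day 21.

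**The case against.** **The wording may only be loose.** SAP 4.2.5.1 sets Day 28 in quotation marks, does not mention Visit 6 in this rule, and sits beside two statements of a 28-day target. A nominal label is a fair reading, so it cannot be said that the plan deliberately chose a variable end point. The gap remains even so: actual times govern the calculation, and nothing says how an early or late sample is brought to 28.0 days.

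**The group-level effect is small.** This stands. No hypothesis is tested, the mean barely moves under even scatter, and the 18-24% shortfall belongs to a visit at the very edge of the window.

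**A remedy may already exist.** SAP 4.2.5.1 allows a population-PK estimate when NCA is not accurate, and a fitted model can give an exact 28-day area. That route is optional, however. An area to Day 21 computes without difficulty, so nothing clearly triggers it.

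**The fix has costs.** Patients whose last samples do not decline are a selected group, mostly early visits with slow absorption. In a stratum of 8, losing one value could use up most of the gain in precision. This is why population PK should be available for them.

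A reader might also infer that the planned comparison with the adult and adolescent model is invalidated. The documents do not support that. Protocol 9.5.3.1 does not say that AUC(0-28) is the quantity compared or that the projection covers 28 days, and the projection described in Protocol 4.3 is of steady-state exposure.

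**Conclusion.** The point holds as a conflict between the derivation rule and the endpoint definition. Followed literally, SAP 4.2.5.1 gives individual areas that are 18-24% low at Day 21 and 13-18% high at Day 35, and no existing provision corrects them. These figures rest on the assumed one-compartment profile, the implied 16.8-day half-life and the assumed absorption range. The textual conflict does not depend on them.

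A reader might infer that the group results for a primary endpoint are seriously biased. The calculation does not support this: with visits uniform over the window, the mean shift is about −1% and a 30% CV becomes about 31.5-33%. The harm is to individual values, range and spread in small strata. It is worth correcting because the endpoint is primary and the correction is cheap.

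**What to change.** In SAP 4.2.5.1, define AUC(0-28) as the partial area from time zero to exactly 28.0 days after the first dose, in line with the abbreviation list.

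- Pre-dose Visit 6 sample later than Day 28: interpolate log-linearly to 28.0 days.
- Pre-dose Visit 6 sample earlier than Day 28: extrapolate to 28.0 days with the terminal slope. The figures above use the slope of the last two quantifiable samples.
- Visit 6 sample missing or not quantifiable, or last samples not declining: do not report an NCA area that ends early. Use the population-PK estimate that SAP 4.2.5.1 already allows, flagged as such, or report the value as not calculated.

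The cost is a short addition to the SAP and one programming rule, with no new data. Early visits carry some extrapolation error. With 10% residual error, a Day 21 patient has a 90% range of about −8% to +12%; with 15% it is −12% to +17%. A few patients will have no NCA value. They include those who enter the NCA set on Days 1, 7 and 14 only, who are not counted in the 0.2-7% above because that figure assumes every patient has a Visit 6 sample.

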4.2.5.2 Summary Statistics of PK serum concentrations

Serum concentrations will be presented by assessment day in tables and listings. The serum concentrations summaries will include:

- n
- $n < LLOQ$ ((n < LLOQ)/n at time point) *100%
- Gmean (gCV%)
- gSD Amean
- arithmetic standard deviation (SD), median (min, max)

For DXD, only the PK samples collected within one dosing cycle after last dose will be included in the summary statistics of schedule visits during treatment period.

The exclusion of concentration data from the PK analysis for an individual time point will be documented by the PK Scientist including the reason(s) for exclusion. These individual concentration data will also be excluded from the summary tables and corresponding figures.

For those patients eligible for inclusion in the PK Analysis set, the concentration-time data will be summarised by the scheduled time point. Any post-dose samples taken outside the window of the scheduled time will be flagged by the PK Scientist and excluded from the summary tables and figures but will be included in the PK analysis to determine the PK parameters.

Serum concentrations that are <LLOQ will be reported as follows:

Individual concentrations below the LLOQ of the bioanalytical assay are non-quantifiable and will be reported as <LLOQ in the listings with the LLOQ defined in the footnotes of the relevant tables, figures and listings. Non-reportable individual concentrations that is a PK parameter (e.g. C_{max}) will be listed as not reportable (NR) and concentrations that are missing

will be listed as no sample (NS) in the listings. Serum concentrations that are <LLOQ, NR or NS will be handled as follows for the provision of descriptive statistics:

- Any values reported as NR or NS will be excluded from summary tables and figures.
- All <LLOQ values will be substituted with a value of zero, and will be excluded from summary descriptive statistics.
- If all concentrations are <LLOQ at a time point, no descriptive statistics will be calculated for that time point. The Gmean, Amean, SD, min, median and max will be reported as <LLOQ and the gCV%, gSD, and SD as not calculated (NC).
- The number of <LLOQ values, n will be reported for each time point along with the total number of collected values (n).

The serum PK concentration data for benralizumab will be displayed graphically. For DXD, only the scheduled PK samples collected within one dosing cycle after last dose will be included in the mean serum-concentrations time profiles graphs. Figures for the Gmean (gSD) concentration-time data will be presented on both a linear and semi-logarithmic scale. Individual concentration time will be graphically presented on linear and semi-logarithmic scales. <LLOQ samples will be plotted as LLOQ with footnote in the graphs.

Displays will include:

- Individual patient serum concentration-time profiles on the linear and semi-log scale showing single dose on Day 1, 2, 7, 28 on same plot, stratified by treatment/weight groups and color-coded by ADA status.
- Gmean serum concentration-time profiles (with gSD error bars) on the linear and semi-log scale showing single dose on Day 1, 2, 7 and 28, stratified by treatment/weight groups
- Serum trough concentrations boxplots to include median and n values on the plot
 - n will be reported for each time point

Precision and rounding rules for PK concentration data

PK concentration data listings will be presented to the same number of significant figures as the data received from the bioanalytical laboratory. PK concentrations descriptive statistics will all be presented to 2 decimal places with the exception of n and number of <LLOQs which will be presented as integers.

